3.9.2 Biological measures of Alcohol and other substance use

Urine drug screens (UDS). Participants will be asked to provide a urine sample for UDS at the baseline visit. The results will be used as an objective measure of recent drug use to supplement self-reported measures. Results will be issued as either positive or negative for a substance; no quantification of the concentration of the substance in the urine will be given. UDS will be obtained at baseline and at all follow up assessments.

Ethyl Glucuronide (EtG). Participants will be asked to provide a urine sample to assess EtG at baseline, 4, 8 and 12 weeks. Results will be correlated with self-report measures of alcohol use and GGT in order to test the hypothesis that changes in alcohol consumption and GGT will be reflected by changes in EtG. EtG is a direct metabolite of alcohol; it remains in urine

for up to 5 days after cessation from alcohol, is highly sensitive and has good specificity for alcohol use (65).

Ethyl Sulfate (EtS): Participants will be asked to provide a urine sample to assess EtS at baseline, 4, 8 and 12 weeks. EtS is a direct metabolite of alcohol; it remains in urine for up to 5 days after cessation from alcohol, is highly sensitive and has good specificity for alcohol use (65). Additionally, we are already collecting urine for EtG and the laboratory that tests for EtG is already combining the EtS with EtG at no additional cost.

Gamma-glutamyl transferase (GGT): is an enzyme that transfers gamma-glutamyl functional groups. It is found in many tissues, the most notable the liver, and has significance in medicine as a diagnostic marker of alcohol use (66).

Alanine Aminotransferase (ALT): is an enzyme that converts alanine into pyruvate. It is mainly found in the liver and be increased with liver injury.

Aspartate Aminotransferase (AST): is a pyridoxal phosphate-dependent transaminase enzyme that catalyzes the reversible transfer of an α -amino group between aspartate and glutamate. It is mainly found in the liver and may be increased with liver injury. An AST to ALT ration of 2:1 is suggestive of alcohol related liver injury (66).

Creatine Kinase (CK): is an enzyme expressed in various tissues and as a blood test is a marker of muscle injury.

3.9.3 Laboratory Safety Measure

B-type natriuretic peptide (BNP): is a hormone secreted by cardiomyocytes in response to stretching caused by increased ventricular blood volume. A plasma BNP (≤ 100 ng/L) provides an excellent ability to exclude heart failure with high sensitivity (67).

3.9.4 Inflammatory Markers

C-Reactive protein (CRP): is a protein found in the blood plasma that rises in response to inflammation. CRP will be assessed to check inflammatory responses to pioglitazone. Other inflammatory markers such as interleukin-6,8 and 12 as well as tumor necrosis factor- alpha and SB100 a marker of blood brain barrier inflammation will be tested. One of pioglitazone's purported mechanism of action is via inflammation thus we will test for these markers.

3.10 Potential hazards to personnel and precautions: Collection of blood and urine samples may pose a hazard to study personnel. Contact with blood or urine has the potential to transmit disease. The collection of blood will be performed in the existing Minneapolis and Long Beach VAHCS laboratories where lab technicians are already trained and utilize universal precautions. The collection of urine samples will be completed in the clinics by research staff. All staff will be trained in universal precautions and the study will comply with all safety regulations and training stipulated by VA.

3.11 Follow-up: At each visit, research coordinators will administer all measures, dispense medication and deliver the BBCET. Any concerning side effects or lab abnormalities will be reviewed with the PI or site PI. Appropriate medical evaluation will be undertaken as deemed necessary by the PI's. Subjects who miss three consecutive visits will stop the medication as they will have been off of medication for minimum of 1 week. Any serious adverse side effects where the blind needs to be broken will result in stopping the assigned treatment. However, every effort will be made to gather research data through the end of the study.

3.12 Randomization: Participants will be randomly assigned to one of two groups (pioglitazone or control/ placebo) using a minimization method of Pocock and Simon (1975)(68). Randomization will be stratified by site (Minneapolis and Long Beach) and will be handled centrally by the Data Coordinating Center at the Minneapolis VA, and a special randomization program will be developed in consultation with a statistician in Minneapolis ([name]). The program will track the balance of stratification variables (i.e., site) for each condition and change the probability of assignment if the variables are unbalanced. This method assures that the two groups are comparable with respect to the stratification variables throughout the study period.

Each site will be provided a number of envelopes with randomization results sealed inside. Privacy envelopes will ensure that the results cannot be detected without breaking the seal. The envelopes will be numbered and will be opened in that order. The number of envelopes will be the number of expected enrollees plus 10 extra in order to account for non-compliant participants and dropouts. These envelopes will only be opened by the research pharmacist. This procedure will be used to maintain the blind for the PI, research assistants, study coordinators and therapists. Only the research pharmacy will be allowed to know the randomization for each participant. The pharmacist will keep all envelopes containing the randomizations. When a subject signs the informed consent form, the pharmacist will be called and asked to select the next envelope and open it, fill out the participant number and dispense study medication according to the randomization. If a physician or medical professional needs to know whether the patient is taking the study drug, a wallet card given to the participant will contain the number of the research pharmacy. The professional can call the pharmacy to access the list of participants and can break the blind for that participant.

Statistical Considerations

4.0 Data Analysis Plan

4.1 Data Management.

Study data will be collected and managed using VA REDCap (Research Electronic Data Capture) hosted behind the VA firewall on a VINCI server. REDCap is a secure, web-based application designed to support data capture for research studies, providing 1) an intuitive interface for validated data entry; 2) audit trails for tracking data manipulation and export procedures; 3) automated export procedures for seamless data downloads to common statistical packages; and 4) procedures for importing data from external sources.

4.2 Data quality/integrity.

All data will be obtained by an assessor (the research coordinator) who will be blinded to the treatment condition. All data will be inspected for missing and outlier values and response set patterns. Distributions will be graphically represented and inspected visually and quantitatively for departures from normality and other irregularities. All data will be characterized in terms of means, standard deviations, histograms, and response ranges for continuous variables and frequencies and counts for categorical variables. A random sample of 5% of

cases will have all hard copy data compared to entered data for accuracy, including all measures scored by computer algorithms. The need for data re-entry or recoding, data transformations and non-linear or non-parametric analyses will be based on these results.

4.3 Descriptive analyses

To confirm that the randomization scheme achieved the intended aim of evenly distributing important study characteristics, groups will be statistically compared on baseline demographic and clinical variables. Any significant group differences on these baseline variables will be factored into study analyses (e.g., using covariates).

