4.4 Primary and secondary outcome measures

For the primary outcome we will use change in number of heavy drinking days per week. Secondary outcome measures will include a responder analysis, the rate of no heavy drinking over the last 8 weeks of the study, and another continuous measure of alcohol use including number of drinks per week over the entire study period. Heavy drinking days per week was chosen as it is a standard outcome used previously used in clinical AUD trials (34, 55). The responder analysis measure of no heavy drinking days over the last 8 weeks of the active study period (weeks 6-14) was chosen as a secondary outcome as it was recently recommended by the FDA in their guidance to industry for the development of drugs for alcoholism (35). The FDA report indicated that a responder analysis is preferable to analysis of group means as mean differences are difficult to interpret with regard to clinical relevance. In addition, changes in this measure is associated with good clinical outcomes (35). Each subject will be assessed for the outcome variables (alcohol consumption) at baseline (date of randomization), 1,2,3,4,6,8,10,12 and 14 weeks (week 16 is a safety check as medications will be tapered off starting at week 14). For the responder analysis, we will use Chi -square to test the difference between pioglitazone and placebo for the rate of no heavy drinking over the last 8 weeks (week 6-14) of the study. Hypotheses will also be tested across all time points to establish temporal patterns of group effects. For the continuous measures of alcohol use we will use mixed effects models if data residuals are normally distributed and generalized estimating equations (GEE) if the data are non-normally distributed (69, 70). Both are flexible regression methods for incomplete repeated measures data and allow continuous and categorical covariates, fixed and time-dependent covariates, and a specification of unstructured as well as structured covariance matrix. Secondary hypotheses will be evaluated using chi-square tests of proportions and logistic regression, with statistical significance criterion also set at $p < 0.05$ for categorical outcomes. Zero-inflated negative binomial analyses will be used to contrast the study groups on count variables if warranted by a high percentage of zero alcohol use days over the follow-up (71).

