4.5 Power Estimate

The primary intention to treat population will include all participants randomized. The effect size of pioglitazone is estimated based on studies. Schmitz et al found a small effect size favoring pioglitazone (94% likelihood of decrease in alcohol use versus 83% in placebo) which is likely low as all the subjects studied had a primary cocaine use disorder diagnosis with an AUD secondary. Based on a sample of Veterans at the Minneapolis VAHCS who had taken

pioglitazone during fiscal year 2016 we found that taking pioglitazone was associated with decreased alcohol use as measured by the AUDIT-C with an effect size of $d=.48$.

Using G*power we estimated sample size for various base rates of drinking (heavy drinking days per week) by various differences in reductions in rate produced by pioglitazone versus placebo across the 14 weeks follow-up period using Poisson regression. Baseline heavy drinking days per week in our Baclofen study, was 3.5 per week. Based on this we estimate that we are adequately powered to find clinically meaningful differences in reduction (20% or greater) given our proposed sample size.

Base Rate per week (Heavy Drinking Days)	Reduction in rate.	Power	Total N
4	19%	80%	164
3	19%	80%	217
2	19%	80%	321
4	20%	80%	147
3	20%	80%	194
2	20%	80%	288
4	21%	80%	132
3	21%	80%	175
2	21%	80%	260
4	22%	80%	120
3	22%	80%	159
2	22%	80%	235
4	23%	80%	109
3	23%	80%	145
2	23%	80%	214

Thus, we feel that the sample size of 200 (100 per site) is still warranted.

For **secondary outcomes** including the categorical outcome (no heavy drinking days in the last 8 weeks of the study) with 90 patients in each group (100 recruited subjects in each group, assuming 20% attrition) we estimate that this sample size will allow us to find a 22% difference (OR=2.45) in heavy drinking days with 80% power at $p<.05$. Both mixed models and GEE allow us to take full advantage of the ITT sample and thus power is based on 90 subjects per group. Other secondary measures including biomarkers of alcohol use (EtG/EtS and GGT) and for craving we will use linear mixed models to compare change in biomarkers and change in OCDS scores. Estimates for comparisons of these continuously distributed outcomes indicate

that we will be able to find effect sizes of $d=.47$ with 72 subjects or larger with 100 subjects per group.

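### Covariates are to be chosen by testing the arms for baseline differences, so the adjusted model depends on chance imbalance; neither baseline drinking nor site is prespecified as a covariate

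*Combined protocol and SAP*

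**What the plan says.** Section 4.3 (Descriptive analyses) has the arms compared statistically on baseline characteristics and then states: "Any significant group differences on these baseline variables will be factored into study analyses (e.g., using covariates"). It gives no list of variables, no significance level and no fixed method of adjustment.

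Section 4.4 names no covariate for any efficacy model. It says only that mixed models and GEE "allow continuous and categorical covariates, fixed and time-dependent covariates".

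Baseline drinking does appear in Section 4.4 in two other ways. The primary outcome is a change: "For the primary outcome we will use change in number of heavy drinking days per week". Baseline is also one of the outcome time points: "Each subject will be assessed for the outcome variables (alcohol consumption) at baseline (date of randomization"). The plan does not say whether baseline is subtracted, modelled as a time-0 response or adjusted for.

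The responder outcome is analysed by a chi-square test "to test the difference between pioglitazone and placebo for the rate of no heavy drinking over the last 8 weeks". Logistic regression is mentioned without covariates: "Secondary hypotheses will be evaluated using chi-square tests of proportions and logistic regression".

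Section 3.12 makes site the only factor balanced by the minimization. No section puts site into a model.

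**The concern.** A covariate earns its place by predicting the outcome. A significance test between randomized arms measures only chance imbalance, so the rule selects on the wrong property. Pre-treatment drinking is the obvious candidate predictor of later drinking, and site is the factor that the allocation is built around. These two have the clearest case for inclusion, and the rule will normally not bring either in.

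Two things are at stake. First, the model is not fixed in advance. The covariate set depends on which imbalances appear, and the comparison needs treatment codes; the timeline in Section 6.0 places unblinding just before analysis. Second, precision may be lost. Section 4.5 leaves little slack: at 3 heavy drinking days per week and a 20% reduction its table needs 194 of the planned 200, and at 19% it needs 217.

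**Working it through.** **Inputs from the documents.** 200 participants, 100 per site (Section 4.5), hence 100 per arm; two sites balanced by minimization (3.12); responder planning values of a 22-point difference, OR 2.45, 90 per arm and 20% attrition (4.5).

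**Assumed inputs.** Baseline tests at two-sided 5%; minimization assignment probability 0.6 to 0.9; baseline-to-follow-up correlation r = 0.3 to 0.7; baseline/follow-up SD ratio k = 1 or 0.7; site R² 0.02 to 0.10; baseline log-odds ratio for response 0.5 or 1.0 per SD. The documents give none of these.

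**1. What the rule selects.** Under valid randomization a 5% test selects baseline drinking in 5% of trials, whatever its prognostic value (simulated: 4.7% to 5.2%). Site differed significantly between arms in 0 of 4,000 simulated trials at each assignment probability; with no balancing at all it would do so in 5.5%. If m independent variables are screened, at least one enters by chance with probability 1 − 0.95^m: 40% for m = 10 and 64% for m = 20 (less if they are correlated).

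**2. Type I error.** In simulations with 100 per arm, test-then-adjust gave 3.4% to 5.1%. There is no inflation.

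**3. Baseline as covariate against a change score.** Linear model, one baseline and one follow-up value:

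variance ratio = (1 − r²)/(1 + k² − 2rk); power = Φ(2.80/√ratio − 1.96), where the change score has 80%.

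| r | ratio, k = 1 | power | ratio, k = 0.7 | power |
|---|---|---|---|---|
| 0.3 | 0.91/1.40 = 0.65 | 93.5% | 0.91/1.07 = 0.85 | 86.0% |
| 0.5 | 0.75/1.00 = 0.75 | 89.9% | 0.75/0.79 = 0.95 | 82.0% |
| 0.7 | 0.51/0.60 = 0.85 | 86.0% | 0.51/0.51 = 1.00 | 80.0% |

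The inclusion criteria set a floor on baseline drinking, so k below 1 is plausible. If baseline is a repeated measure with a common mean across arms, fixed adjustment gains nothing.

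**4. Whether the trigger recovers the loss.** Simulated power at k = 1 and r = 0.3, 0.5, 0.7 (10,000 trials per cell): change score 79/80/80%; adjusting only when baseline differs significantly 81/81/80%; always adjusting 93/89/86%. The trigger recovers little.

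**5. Omitting site.** When site is balanced but left out, the model overstates the standard error by 1/√(1 − R²). The effective critical value becomes 1.96/√(1 − R²), and power is Φ(2.80 − that value).

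| site R² | critical value | power (80% with site) | type I error |
|---|---|---|---|
| 0.02 | 1.98 | 79.4% | 4.8% |
| 0.05 | 2.01 | 78.5% | 4.4% |
| 0.10 | 2.07 | 76.9% | 3.9% |

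**6. Responder outcome.** Section 4.5 says that "this sample size will allow us to find a 22% difference (OR=2.45) in heavy drinking days with 80% power". Its two figures fix the lower rate p: (p + 0.22)(1 − p) = 2.45 p(0.78 − p), so 1.45p² − 1.131p + 0.22 = 0 and p = 0.371 or 0.409. The stated 90 per arm is roughly reproduced: 36% against 58% (OR 2.455) needs 80 per arm without and 89 with continuity correction. Losing 20% of 100 leaves 80, so both sizes were simulated (4,000 trials per cell; logistic model with baseline and site, no true site effect):

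| per arm | lower rate | log-OR 0.5: chi-square / logistic | log-OR 1.0: chi-square / logistic |
|---|---|---|---|
| 90 | 0.371 | 82.5 / 85.4% | 83.3 / 90.2% |
| 90 | 0.409 | 82.8 / 86.3% | 83.3 / 90.5% |
| 80 | 0.371 | 80.3 / 82.4% | 77.9 / 86.3% |
| 80 | 0.409 | 79.9 / 82.1% | 79.4 / 87.1% |

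The gain is about 2 to 8 points. It is a gain in power only: at 90 per arm the median standard error of the log-odds ratio rises from 0.307 to 0.320 or 0.347, because the conditional effect is larger.

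**The case against.** The strongest reply is that silence is not exclusion. Section 4.3 sits under descriptive analyses and says that imbalanced variables will be used, not that no others may be. Site is arguably not the kind of characteristic it screens, and Section 4.4 notes that the models accept covariates. This stands in part: the text does not forbid either covariate. But it commits to neither, and the one rule it states is the wrong one.

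A reader might infer that baseline drinking is kept out of the efficacy analyses. The documents do not support that: the primary outcome is a change, and baseline is a listed outcome time point. What is missing is a statement of how it enters. Only the responder chi-square uses no baseline information on any reading.

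A reader might also take 93% against 80% as the trial's loss. That is the top of an assumed grid for a single-follow-up linear model. The plan has nine follow-up visits analysed by mixed model or GEE, with a count alternative: "Zero-inflated negative binomial analyses will be used to contrast the study groups on count variables". Change scores can be negative, so that model cannot be fitted to them. If the comparator is unadjusted follow-up, the ratio is 1 − r² and power is 84/90/98% at r = 0.3/0.5/0.7, so the gain rises with r instead of falling. Even the direction depends on a model that the plan has not fixed.

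Finally, the unadjusted chi-square is valid and matches the difference in proportions that was powered. That stands, and is why it should be kept.

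**Conclusion.** The concern holds as a matter of prespecification and efficiency, not of validity. A reader might infer bias or an inflated false-positive rate from the trigger rule; neither is supported, and leaving out the balanced factor site makes the test slightly conservative.

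The firmest harm needs no assumed correlation: the covariate set is decided by chance imbalance after the arms are compared, from an unlisted set of variables at an unstated level. The selection rates for baseline drinking and site rest on an assumed 5% level.

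The loss of precision is real in principle but of uncertain size: from nothing to about 13 power points for the primary outcome in the simple linear illustration, about 0.6 to 3 points for site, and about 2 to 8 points for the responder outcome. All of these rest on assumed SD ratios, correlations, site effects or prognostic strengths. The change should be made, because the better method costs almost nothing.

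**What to change.** - Delete the significance trigger in Section 4.3 and report baseline characteristics descriptively by arm.
- In Section 4.4, prespecify site and baseline heavy drinking days per week as fixed covariates in the primary mixed, GEE or count model. Take the baseline value from one stated part of the three-month TLFB look-back.
- If the zero-inflated model is used, model follow-up counts rather than change scores, and say which parts of the model carry the covariates.
- If baseline is instead kept as a time-0 response, say so, give both arms a common baseline mean, include site, and do not also enter baseline as a covariate.
- In each continuous secondary model, use site and the matching baseline value.
- For the responder outcome, keep the response rates and the chi-square. Add the logistic regression already named, adjusted for baseline drinking and site, with a standardized risk difference.
- Treat adjustment for observed imbalances as a sensitivity analysis.

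Cost: SAP wording only, since site and the TLFB look-back are already collected by randomization. The downside is that the adjusted odds ratio is conditional and is not the same quantity as the difference in response rates, so both estimates must be reported.

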4.4 Primary and secondary outcome measures

For the primary outcome we will use change in number of heavy drinking days per week. Secondary outcome measures will include a responder analysis, the rate of no heavy drinking over the last 8 weeks of the study, and another continuous measure of alcohol use including number of drinks per week over the entire study period. Heavy drinking days per week was chosen as it is a standard outcome used previously used in clinical AUD trials (34, 55). The responder analysis measure of no heavy drinking days over the last 8 weeks of the active study period (weeks 6-14) was chosen as a secondary outcome as it was recently recommended by the FDA in their guidance to industry for the development of drugs for alcoholism (35). The FDA report indicated that a responder analysis is preferable to analysis of group means as mean differences are difficult to interpret with regard to clinical relevance. In addition, changes in this measure is associated with good clinical outcomes (35). Each subject will be assessed for the outcome variables (alcohol consumption) at baseline (date of randomization), 1,2,3,4,6,8,10,12 and 14 weeks (week 16 is a safety check as medications will be tapered off starting at week 14). For the responder analysis, we will use Chi -square to test the difference between pioglitazone and placebo for the rate of no heavy drinking over the last 8 weeks (week 6-14) of the study. Hypotheses will also be tested across all time points to establish temporal patterns of group effects. For the continuous measures of alcohol use we will use mixed effects models if data residuals are normally distributed and generalized estimating equations (GEE) if the data are non-normally distributed (69, 70). Both are flexible regression methods for incomplete repeated measures data and allow continuous and categorical covariates, fixed and time-dependent covariates, and a specification of unstructured as well as structured covariance matrix. Secondary hypotheses will be evaluated using chi-square tests of proportions and logistic regression, with statistical significance criterion also set at $p < 0.05$ for categorical outcomes. Zero-inflated negative binomial analyses will be used to contrast the study groups on count variables if warranted by a high percentage of zero alcohol use days over the follow-up (71).

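### Section 4.3 lets baseline significance tests choose the covariates, so the primary analysis need not adjust for baseline heavy drinking days or site

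*Combined protocol and SAP*

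**What the plan says.** **Outcome and model.** Section 4.4: "For the primary outcome we will use change in number of heavy drinking days per week". For continuous measures, "we will use mixed effects models if data residuals are normally distributed and generalized estimating equations (GEE) if the data are non-normally distributed". Of the two methods it says "Both are flexible regression methods for incomplete repeated measures data", and that they can take covariates and structured or unstructured covariance. It chooses none of these. A further branch is conditional: "Zero-inflated negative binomial analyses will be used to contrast the study groups on count variables if warranted". On time points: "Hypotheses will also be tested across all time points to establish temporal patterns of group effects".

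**Covariates.** The only rule is in section 4.3: "Any significant group differences on these baseline variables will be factored into study analyses". Section 4.2 adds that "data transformations and non-linear or non-parametric analyses will be based on these results".

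**What is available.** Section 3.12 uses minimisation with site as the only balancing factor. Under section 3.9.1 the TLFB covers the three months before treatment and the intervals between assessments, so baseline heavy drinking days are already collected.

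**Power.** Section 4.5 uses Poisson regression over the 14-week follow-up, with a baseline of 3.5 heavy drinking days per week, a reduction of 20% or more and 200 patients.

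**Responder outcome.** Section 4.4 uses a chi-square "to test the difference between pioglitazone and placebo for the rate of no heavy drinking over the last 8 weeks". Section 4.7 includes everyone randomised, but treats responses after withdrawal as missing.

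**The concern.** In a randomised trial, baseline differences between arms arise by chance. A significance test on them does not show whether a covariate is worth including. That depends on how strongly it predicts the outcome, and prior drinking should predict later drinking well. Under the 4.3 rule, the most useful covariate enters only in the few trials where it happens to be imbalanced. Site may be omitted although the allocation balances on it, and leaving out a balancing factor that predicts the outcome tends to overstate the standard error.

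Taking the word change literally does not solve this. A change score subtracts baseline with a coefficient of one, which adds noise unless the correlation is high. At stake are power for the primary comparison and a primary model that is the same whatever the baseline table shows.

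**Working it through.** **1. The plan's own figures.** The primary table in 4.5 has a base rate, a reduction and a total N, but no covariate and no baseline correlation. It therefore cannot show what adjustment is worth. The responder figure can be reproduced. A 22-point difference with OR 2.45 implies about 39% v 61%, since (0.61/0.39)² = 2.45. Two-sided at 0.05 with 80% power:

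n = [1.96·√(2·0.5·0.5) + 0.8416·√(0.39·0.61 + 0.61·0.39)]² / 0.22² = 79.9, so 80 per group, or 89 with continuity correction, against the plan's 90.

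**2. Why adjustment helps.** With equal baseline and follow-up variance σ² and correlation ρ between the observed averages:
- change score variance: 2σ²(1 − ρ)
- baseline-adjusted variance: σ²(1 − ρ²)
- ratio: 2/(1 + ρ), which is 1.54 at ρ = 0.3, 1.33 at 0.5 and 1.05 at 0.9.

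Adjustment is never worse in large samples, and the gain falls as ρ rises.

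**3. Size, by simulation.** From the plan: 100 per arm, 20% attrition (random here), the visit weeks, a baseline of 3.5 and a 20% reduction. Assumed: weekly counts binomial out of 7, logit random intercept and slope, and intercept correlation 0.5 between baseline and follow-up. The adjusted analysis is an exchangeable GEE with robust standard errors, on the linear and log scales; 1,000 trials per cell.
- A: SDs 1.5/0.6, week-1 mean 3.4, logit fall 0.6
- B: SDs 2.0/1.0, otherwise as A
- C: SDs 1.5/0.6, week-1 mean 3.1, logit fall 1.8

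| Scenario | Immediate effect: adjusted average (linear/log) | Immediate effect: change score | Effect builds to week 6: adjusted average (linear/log) | Effect builds to week 6: change score |
|---|---|---|---|---|
| A | 77.5/77.8% | 57.3% | 74.7/77.3% | 58.0% |
| B | 64.8/65.3% | 45.6% | 63.5/65.2% | 49.1% |
| C | 51.8/47.0% | 30.5% | 55.9/58.7% | 34.0% |

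On the linear scale with an immediate effect the gaps are 77.5 − 57.3 = 20.2, 64.8 − 45.6 = 19.2 and 51.8 − 30.5 = 21.3 points. With no true effect (A), tests rejected in 2.8-6.0% of 600 trials. A simpler regression on visit averages gave 81% v 63% (A) and 70% v 51% (B). In a further run with correlations from 0.3 to 0.9, adjustment won every time; at 0.5 it gave 69-78% v 53-59%. No figure was computed for site.

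**4. What the 4.3 rule recovers.** Section 4.3 states no level. At 5%, baseline heavy drinking days would enter in about 1 trial in 20. Roughly, 0.05 × (69 − 53) = 0.8 and 0.05 × (78 − 59) = 0.95 points. Simulating the rule gave about 1 point.

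**5. Contrast.** With an immediate effect (A and B), the adjusted average has 65-78% power and treatment-by-linear-week 8-24%. If the effect builds to week 6, the trend test has 80-94% against 64-77% for the average. In C on the linear scale that order reverses (28.0% v 55.9%).

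**6. GEE and drop-out.** No true effect, 20% attrition, drop-out driven by drinking in one arm only. The rate ratio is 1.08-1.15 under unadjusted independence GEE, 1.01-1.11 with baseline adjustment, and 1.00-1.03 under exchangeable GEE. With the same pattern in both arms, every method lies between 0.991 and 1.005.

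**7. Responder rule.** At 39% v 61% with 20% loss in each arm:
- Completers only, 80 per arm: 80.1% power.
- Missing as non-response, 100 per arm: 0.8 × 39 = 31.2% v 0.8 × 61 = 48.8%, giving 72.2%.

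In a simulated case of drinking-driven drop-out (true rate 38.5%; 14%, 20% and 24% attrition), the difference was off by 5.0, 7.4 and 9.1 points for completers only, by 4.3, 5.9 and 6.9 with missing as non-response, and by 0.0-0.1 with weighting under missing at random.

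**The case against.** **Baseline is already in the outcome.** The outcome is a change, and 4.4 lists baseline among the repeated assessments. A mixed model with baseline as a response and a common baseline mean would recover most of the gain. This stands as a possibility, but nothing in the plan requires that model; an unadjusted change score fits the text equally well.

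**The contrast is not truly open.** Section 4.5 powers over the 14 weeks, 4.4 takes the secondary drinks-per-week measure over the whole study period, and the all-time-points testing is an addition meant to show temporal patterns. This largely stands. A reader might infer that the primary result could be decided at week 14, where simulated power was only 42-46%, but no section names a week-14 test. What is missing is one sentence naming the average as the primary contrast.

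**The normality fork.** A reader might infer that it makes the result arbitrary. It does not: mean difference and rate ratio disagreed about p<0.05 in only 2-5% of simulated trials, residuals can be inspected without arm labels, and section 6.0 puts data cleaning before the blind is broken.

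**Missing data are addressed.** Section 4.7 plans intention to treat, reasons for drop-out, a check of the mechanism and non-random models, and 3.11 promises continued data collection. All of that stands. Running the non-random models whatever the check shows would be a modest preference. None of it, however, gives a chi-square a yes or no for a patient of unknown status.

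**Conclusion.** The point holds for covariates: 4.3 ties adjustment to chance imbalance, so neither baseline heavy drinking days nor site is a required term. For a true 20% reduction at an assumed intercept correlation of 0.5, the cost is the gap between about 65-78% and about 46-59% power. That compares adjustment with the unadjusted change score, one reading the plan permits. The absolute figures rest on assumed variances and are lower in scenario C. The direction held at every correlation tried.

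The other two gaps are smaller. A reader might infer that choosing GEE biases the trial, but the bias in step 6 needs an independence working correlation, which the plan does not name, together with drop-out that relates to drinking differently by arm. A reader might also take from a worst case that the responder difference could be wrong by 6.5, 10.0 or 12.6 points (a true 40% read as 0.40/0.86, 0.40/0.80 or 0.40/0.76). Those are completers-only figures in which only non-responders leave one arm, and dropping patients conflicts with 4.7. The endpoint is secondary, and TLFB can recover some missed intervals. The missing classification rule is nonetheless real. This should be changed; it does not invalidate the design.

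**What to change.** Before unblinding:

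1. Delete the significance-test rule in 4.3. Always include baseline heavy drinking days (from the three-month TLFB) and site in the primary model.
2. Name the treatment effect averaged over the 14-week follow-up as the single primary contrast, matching the period in 4.5. Keep week-by-week and trend tests secondary.
3. If GEE is used, state a non-independence working correlation, for example exchangeable.
4. For the responder chi-square, recover missed intervals by TLFB where possible. Count any observed heavy drinking day in weeks 6-14 as non-response. Handle remaining unknowns by multiple imputation under missing at random, and report missing-as-non-response as a sensitivity analysis.

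The cost is SAP wording and light programming, with no new data collection. There are two trade-offs. The 14-week average may lose power to a trend test if the effect builds slowly, depending on the scenario (step 5). Multiple imputation, like the weighting in step 7, relies on missing at random, which is why the sensitivity analysis sits beside it.
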